8. Patients are allowed to receive, but are not required to receive, three additional cytotoxic regimen for management of recurrent or persistent disease. Hormonal therapies will not count toward the prior regimen limit.
9. Adequate normal organ and marrow function defined by the following laboratory results obtained within 14 days prior to first treatment:
 - Absolute neutrophil count (ANC) $\geq 1.5 \times 10^9/L$ (> 1500 per mm^3)
 - Platelet $\geq 100 \times 10^9/L$ ($>100,000$ per mm^3)
 - Hemoglobin ≥ 9.0 g/dL
 - Serum bilirubin ≤ 1.5 x institutional upper limit of normal (ULN). (Unless Gilbert's Syndrome, for which Bilirubin ≤ 3 x institutional upper limit of normal (ULN) , without concurrent clinically significant liver disease)
 - AST (SGOT)/ALT (SGPT) ≤ 3 x institutional upper limit of normal (ULN) unless liver metastases are present, in which case it must be $\leq 5x$ ULN
 - Serum creatinine ≤ 1.5 x institutional upper limit of normal (ULN)
10. Female subjects must either be of non-reproductive potential (i.e., post-menopausal by history: ≥ 55 years old and no menses for ≥ 1 year without an alternative medical cause; OR history of hysterectomy, OR history of bilateral tubal ligation, OR history of bilateral oophorectomy) or must have a negative serum pregnancy test upon study entry.
11. Subject is willing and able to comply with the protocol for the duration of the study including undergoing treatment and scheduled visits and examinations including follow up.
12. Patients must have been enrolled, or agree to consent to the companion genomic profiling study MSKCC IRB# 12-245. Results must be available before starting treatment on protocol.
13. Patients must have signed an approved informed consent and authorization permitting release of personal information.

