
Hepatitis (elevated LFTs) Infliximab should not be used for management of immune-related hepatitis.
	
Any Elevations in AST, ALT or TB as Described Below
	
General Guidance
	
For Any Grade:
 
 – Patients should be thoroughly evaluate to rule out alternative etiology (e.g, viral hepatitis, disease progression, concomitant medications, worsening of liver cirrhosis [e.g., portal vein thrombosis]). – Monitor and evaluate liver function test: AST, ALT, ALP, and TB. – For hepatitis B + patients: evaluate quantitative HBV viral load, quantitative Hepatitis B surface antigen (HBsAg), or Hepatitis B envelope antigen (HBeAg). – For hepatitis C (HCV) + patients: evaluate quantitative HCV viral load. – Consider consulting Hepatology or Infectious Diseases specialists regarding changing or starting antiviral HBV medications if HBV viral load is >2000 IU/ml. – Consider consulting Hepatology or Infectious Diseases specialists regarding changing or starting antiviral HCV medications if HCV viral load has increased by ≥ 2-fold. – For HCV+ with Hepatitis B core antibody (HBcAb) +: Evaluate for both HBV and HCV as above. –
	
Isolated AST or ALT >ULN and $\leq 5.0 \times$ULN, whether normal or elevated at baseline
	
 • No dose modifications. • If ALT/AST elevations represents significant worsening based on investigator assessment, then treat as described for elevations in the row below. • For all transaminase elevations, see instructions at bottom of shaded area if transaminase rise is not isolated but (at any time) occurs in setting of either increasing bilirubin or signs of DILI/liver decompensation. 	
 –
	
Isolated AST or ALT >5.0xULN and $\leq 8.0 \times$ULN, if normal at baseline
	
Hold study drug/study regimen dose until resolution to AST or ALT $\leq 5.0 \times$ULN.
 
 • If toxicity worsens, then treat as described for 	
 – Regular and frequent checking of LFTs (e.g., every 1 to 3 days) until elevations of these are improving or resolved.

Date:

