
Isolated AST or ALT >2.0×baseline and ≤12.5×ULN, if elevated>ULN at baseline
	
elevation in the row below. If toxicity improves to AST or ALT ≤5.0xULN, resume study drug/study regimen after completion of steroid taper (<10mg prednisone or equivalent).
 
 • Permanently discontinue study drug/study regimen for any case meeting Hy’s law criteria, in the absence of any alternative cause.^b 	
Recommend consult hepatologist; consider abdominal ultrasound, including Doppler assessment of liver perfusion.
 
 – Consider, as necessary, discussing with Clinical Study Lead. – If event is persistent (>2 to 3 days) or worsens, and investigator suspects toxicity to be an imAE, start prednisone 1 to 2 mg/kg/day PO or IV equivalent. – If still no improvement within 2 to 3 days despite 1 to 2 mg/kg/day of prednisone PO or IV equivalent, consider additional workup. If still no improvement within 2 to 3 days despite 2mg/kg/day of IV methylprednisolone, consider additional abdominal workup (including liver biopsy) and imaging (i.e., liver ultrasound), and consider starting additional immunosuppressants. (e.g., mycophenolate mofetil 0.5 – 1 g every 12 hours then taper in consultation with hepatology consult or relevant practice guidelines). Discuss Clinical Study Lead if mycophenolate mofetil is not available. Infliximab should NOT be used.

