
Isolated AST or ALT >8.0×ULN and ≤20.0×ULN, if normal at baseline
 
Isolated AST or ALT >12.5×ULN and ≤20.0×ULN, if elevated>ULN at baseline
	
 • Hold study drug/study regimen dose until resolution to AST or ALT ≤5.0×ULN. Resume study drug/study regimen if elevations downgrade to AST or ALT ≤5.0×ULN and after completion of steroid taper (<10mg prednisone, or equivalent). • Permanently discontinue study drug/study regimen if the elevations do not downgrade to AST or ALT ≤5.0×ULN within 14 days 	
 – Regular and frequent checking of LFTs (e.g., every 1-2 days) until elevations of these are improving or resolved. – Consult hepatologist (unless investigator is hepatologist); obtain abdominal ultrasound, including Doppler assessment of liver perfusion; and consider liver biopsy. – Consider discussing with Clinical Study Lead, as needed. – If investigator suspects toxicity to be immune-mediated, promptly initiate empiric IV methylprednisolone at 1 to 2 mg/kg/day or equivalent. – If no improvement within 2 to 3 days despite 1 to 2 mg/kg/day methylprednisolone IV or equivalent, obtain liver biopsy (if it has not been done already) and promptly start treatment with immunosuppressive therapy (e.g., mycophenolate mofetil 0.5 – 1g every 12 hours then taper in consultation with hepatology consult or relevant practice guidelines). Discuss with study Clinical Lead if mycophenolate is not available. Infliximab should NOT be used.

Isolated AST or ALT >20×ULN,
	
Permanently discontinue study drug/study regimen.
	
Same as above

Date:

	whether normal or elevated at baseline		(except recommend obtaining liver biopsy early)

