11.4.6 Criteria for Hy's Law (FDA Guidance 2009)

- The drug causes hepatocellular injury, generally shown by a higher incidence of 3-fold or greater elevations above the ULN of ALT or AST than the (non-hepatotoxic) control drug or placebo
- Among trial subjects showing such aminotransferase elevations, often with aminotransferases much greater than 3 x ULN, one or more also show elevation of serum total bilirubin to >2 x ULN, without initial findings of cholestasis (elevated serum alkaline phosphatase)
- No other reason can be found to explain the combination of increased aminotransferases and total bilirubin, such as viral hepatitis A, B, or C; pre-existing or acute liver disease; or another drug capable of causing the observed injury.

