17.2.1.5 Other events requiring reporting

Overdose

An overdose is defined as a subject receiving a dose of durvalumab + tremelimumab in excess of that specified in the Investigator’s Brochure, unless otherwise specified in this protocol.

Any overdose of a study subject with durvalumab + tremelimumab, with or without associated AEs/SAEs, is required to be reported within 24 hours of knowledge of the event to the sponsor and AstraZeneca/MedImmune Patient Safety or designee using the designated Safety e-mailbox (see Section 11.4 for contact information). If the overdose results in an AE, the AE must also be recorded as an AE (see Section 11.4). Overdose does not automatically make an AE serious, but if the consequences of the overdose are serious, for example death or hospitalization, the event is serious and must be recorded and reported as an SAE (see Section 11.4). There is currently no specific treatment in the event of an overdose of durvalumab or tremelimumab.

The investigator will use clinical judgment to treat any overdose.

Hepatic function abnormality

Hepatic function abnormality (as defined in Section 11.4) in a study subject, with or without associated clinical manifestations, is required to be reported as “hepatic function abnormal” **within 24 hours of knowledge of the event** to the sponsor and AstraZeneca/MedImmune Patient Safety using the designated Safety e-mailbox (see Section 11.4 for contact

Date:

information), unless a definitive underlying diagnosis for the abnormality (e.g., cholelithiasis or bile duct obstruction) that is unrelated to investigational product has been confirmed.

- If the definitive underlying diagnosis for the abnormality has been established and is unrelated to investigational product, the decision to continue dosing of the study subject will be based on the clinical judgment of the investigator.
- If no definitive underlying diagnosis for the abnormality is established, dosing of the study subject must be interrupted immediately. Follow-up investigations and inquiries must be initiated by the investigational site without delay.

Each reported event of hepatic function abnormality will be followed by the investigator and evaluated by the sponsor and AstraZeneca/MedImmune.

Pregnancy

Maternal exposure

If a patient becomes pregnant during the course of the study, the IPs should be discontinued immediately.

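### For patients with raised baseline AST/ALT, Table 4's isolated-elevation rows give two instructions over one range of values or none over another, and the Hy's law passages are not cross-referenced

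*Combined protocol and SAP*

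**What the plan says.** The hepatitis part of Table 4 (Section 11.1) sorts isolated AST or ALT rises into bands.

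- **First row.** Above ULN and up to 5×ULN, "whether normal or elevated at baseline", dosing is unchanged. There is a discretionary step up: "If ALT/AST elevations represents significant worsening based on investigator assessment, then treat as described for elevations in the row below". Rises that are not isolated are sent elsewhere: "see instructions at bottom of shaded area if transaminase rise is not isolated".
- **Second row.** This has two entries. One is for a normal baseline, above 5 and up to 8×ULN. The other is for a raised baseline: "Isolated AST or ALT >2.0×baseline and ≤12.5×ULN, if elevated>ULN at baseline". Drug is held until AST or ALT is at or below 5×ULN and may resume after any steroid taper. The row also stops drug permanently for a case meeting Hy's law without an alternative cause.
- **Third row.** Above 8 and up to 20×ULN for a normal baseline; for a raised one, "Isolated AST or ALT >12.5×ULN and ≤20.0×ULN, if elevated>ULN at baseline".
- **Fourth row.** Above 20×ULN for any baseline.

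Section 6.2, item 9, admits AST/ALT up to 3×ULN "unless liver metastases are present, in which case it must be" no more than 5×ULN.

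On combined rises, the first bullet of Section 11.4.6 describes Hy's law by a higher incidence of aminotransferase elevation "than the (non-hepatotoxic) control drug or placebo". Section 11.4.3 defines a hepatic function abnormality in one patient: ALT or AST above 3×ULN with bilirubin above 2×ULN. For that abnormality Section 17.2.1.5 says: "If no definitive underlying diagnosis for the abnormality is established, dosing of the study subject must be interrupted immediately".

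**The concern.** The raised-baseline entry in the second row is anchored to the patient's own baseline, while the first row ends at a fixed 5×ULN. These two boundaries coincide only at one baseline value. On either side of it, a result is covered twice or not at all.

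Hepatitis and hepatotoxicity are listed adverse events of special interest (Section 11.4.3), so the instruction should be unambiguous. Whether a patient is held also matters later. Section 11.1 takes patients off study after 28 or more consecutive missed days for drug-related events, unless the Principal Investigator approves an exception. Section 14.0 reports the therapy completion rate and uses the safety profile to help choose between arms if both have exactly 7 responders. Uneven handling of the same laboratory value would feed into those summaries.

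**Working it through.** **Inputs.** Let b be baseline and x the on-study value of the same enzyme, both in ×ULN. Raised baseline means b > 1. Eligibility allows b ≤ 3, or b ≤ 5 with liver metastases (Section 6.2).

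**Bands in Table 4, isolated rises**

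- Normal baseline: (1, 5], (5, 8], (8, 20], above 20. These are contiguous, with no overlap and no gap.
- Raised baseline: (1, 5], (2b, 12.5], (12.5, 20], above 20.

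For raised baselines the first two bands meet exactly only when 2b = 5, that is b = 2.5.

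- If 1 < b < 2.5, then 2b < 5 and values in (2b, 5] lie in both bands. The width is 5 − 2b.
- If b > 2.5, then 2b > 5 and values in (5, 2b] lie in neither. The width is 2b − 5. The 5 to 8×ULN entry does not help, because it is for normal baselines.
- The largest 2b is 2 × 5 = 10, below 12.5, so the second band is never empty.

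| b | 2b | Two rows apply | No liver row applies |
|---|---|---|---|
| 1.2 | 2.4 | 2.4 to 5.0 (width 2.6) | none |
| 1.5 | 3.0 | 3.0 to 5.0 (width 2.0) | none |
| 2.0 | 4.0 | 4.0 to 5.0 (width 1.0) | none |
| 2.4 | 4.8 | 4.8 to 5.0 (width 0.2) | none |
| 2.5 | 5.0 | none | none |
| 2.6 | 5.2 | none | 5.0 to 5.2 (width 0.2) |
| 3.0 | 6.0 | none | 5.0 to 6.0 (width 1.0) |
| 4.0 | 8.0 | none | 5.0 to 8.0 (width 3.0) |
| 5.0 | 10.0 | none | 5.0 to 10.0 (width 5.0) |

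Lower limits are excluded and upper limits included. For a given baseline value only one of the two problems can arise. In the overlap, the level that releases the hold (≤ 5×ULN) is already met when the hold begins.

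**Combined rises, side by side**

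- Table 4: permanent stop if Hy's law is met and no alternative cause exists. In the text available, it appears in a row for isolated rises, although Hy's law needs raised bilirubin.
- Section 11.4.6: bullet 1 compares incidence with a control or placebo. Both arms here receive durvalumab, so no such comparator exists. Bullets 2 and 3 give the laboratory pattern, absence of initial cholestasis, and no other explanation.
- Section 11.4.3: a patient-level pattern with no cholestasis condition.
- Section 17.2.1.5: interrupt and investigate when no definitive diagnosis is established.

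Table 4's stop and Section 17.2.1.5 are not tied to each other, and the two patterns that trigger them are not identical.

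**The case against.** **On the rows.** Section 11.1 calls its instructions guidelines. The first row lets the investigator move a patient to the next row, and in the overlap the hold is released as soon as it starts. In the gap, general text remains. Table 4's opening block gives actions by grade, and Section 11.3 requires a delay for non-hematologic toxicity of Grade 2 or above that affects organ function. Up to b = 3 the gap is at most 1×ULN wide; wider gaps need liver metastases.

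Much of this is fair, and it limits the consequences. It does not remove the inconsistency. The step up is discretionary, whereas the second row applies without discretion, and the step up belongs to a row ending at 5×ULN, so it cannot reach the gap. For Grade 3 the opening block sends the reader back to the specific rows. Section 11.3 depends on an effect on organ function and ends the delay at Grade 1 or baseline, a different release condition from Table 4's 5×ULN.

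**On Hy's law.** A reader might infer three stronger things, which the documents do not support.

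- That no patient could be tested against the stop. Only bullet 1 of Section 11.4.6 is a drug-level comparison, and it is worded as what is generally seen. Bullets 2 and 3 can be checked in one patient.
- That Table 4 and Section 17.2.1.5 contradict each other. They can be read in sequence: interrupt, investigate, then discontinue if no alternative cause is found.
- That a patient with ALT 4×ULN and bilirubin 2.5×ULN could simply continue under the first row. That row covers isolated rises only, and Section 17.2.1.5 leaves continuation to the investigator only after an unrelated diagnosis is established.

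The instructions for non-isolated rises and the footnote marked at the Hy's law sentence are absent from the text available. They may have been lost when the PDF was read, so they are not counted as errors.

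**Conclusion.** The point holds for the isolated AST/ALT rows. Read literally, every raised baseline other than exactly 2.5×ULN produces either a range with two instructions or a range with no liver-row instruction, and eligible patients can reach both. The overlap runs from 2b to 5×ULN and the gap from 5×ULN to 2b, reaching 10×ULN at the entry limit with liver metastases. This assumes that the two entries of the second row share one action, as the extracted table suggests, and that baseline and on-study values refer to the same enzyme.

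The Hy's law material supports a lesser conclusion: four related passages lack cross-references and do not share one definition.

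This should be fixed, but no ORR or PFS decision rule or error rate depends on it. The documents do not say how many patients have raised baseline values, so the effect on holds, discontinuations or hepatic event rates cannot be estimated.

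**What to change.** Reconcile the raised-baseline AST/ALT rows of Table 4 so that every value has exactly one instruction over the full entry range, up to 3×ULN and up to 5×ULN with liver metastases. Cross-reference the Table 4 Hy's law instruction with Sections 11.4.3, 11.4.6 and 17.2.1.5, so that a reader can tell which definition triggers which step and in what order. The clinical team decides which action, threshold and definition apply.

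The cost is amendment wording. No new assessment is needed: the comprehensive profile, which includes AST, ALT and total bilirubin (Section 8.1), is already scheduled on Days 1 and 15 of each cycle (Section 10.0).
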